## 2 Synopsis

Name of Sponsor/Company: Dow Pharmaceutical Sciences, a division of Valeant Pharmaceuticals North America, LLC
Name of Investigational Product: IDP-120 Gel
Name of Active Ingredients: tretinoin and benzoyl peroxide [BPO] gel, 0.05%/2.5%
Title of Study: A Phase 3, Multi-Center, Randomized, Double-Blind, Vehicle-Controlled, 2 Arm, Parallel Group Study Comparing the Safety and Efficacy of IDP-120 Gel and IDP-120 Vehicle Gel in the Treatment of Acne Vulgaris
Number of clinical centers: Multicenter, approximately 24-35 investigational centers in North America and Latin America
Objective: The primary objective of this study is to compare the safety, efficacy and tolerability of IDP-120 Gel and IDP-120 Vehicle Gel in the treatment of subjects with moderate to severe acne vulgaris.
Methodology: This is a multi-center, randomized, double-blind, vehicle-controlled, 12-week study designed to assess the safety, tolerability, and efficacy of IDP-120 Gel and IDP-120 Vehicle Gel at Weeks 2, 4, 8, and 12. To be eligible for the study subjects must be at least 9 years of age and have a clinical diagnosis of moderate to severe acne (defined as an EGSS score of 3 or 4), presenting with 20-50 inflammatory facial lesions (papules, pustules, and nodules), 25-100 non-inflammatory facial lesions (open and closed comedones), and $\leq$ 2 facial nodules.  Approximately 600 subjects will be randomized to the following treatment groups: 
 
• 300 Subjects to IDP-120 Gel, once-daily application
 
• 300 Subjects to IDP-120 Vehicle Gel, once-daily application
 
 All subjects will receive once daily, topically-applied treatment to the face for 12 weeks. Subject visits include Screening, Baseline, Week 2, Week 4, Week 8, and Week 12, at which safety and efficacy assessments will be conducted. Study drug will be dispensed to the Subjects at Baseline, Week 4 and Week 8. Subjects will be evaluated for drug usage compliance at each post-baseline study visit (Weeks 2, 4, 8, and 12). Subjects will apply their treatments at home, once daily in the evening, as instructed by the study coordinator or designee at each investigational center (with the exception of study visit days, where study drug will be applied by the subject on-site during the study visit).  The investigator will assess the subject's face at each study visit. Information on reported and observed AEs will be obtained at each visit. An abbreviated physical exam and vital signs measurement will be performed at Baseline and Week 12 (Final Visit) visits for all subjects. Blood samples will be collected from subjects at Baseline and Week 12, for CBC/Diff, serum chemistry, and serum pregnancy (for pre-menses females and females of childbearing potential). For all pre-menses females and females of childbearing potential (FOCBP), urine pregnancy testing will be performed at Screening, Baseline prior to randomization, and at Weeks 2, 4, 8, and 12. All subjects will also be asked to complete the Acne-Specific Quality of Life Questionnaire at Baseline and Week 12. In addition, at selected sites, standardized photography of the face will be performed at Baseline and Weeks 2, 4, 8 and 12.
Number of subjects planned: Approximately 600 subjects with moderate to severe acne vulgaris will be enrolled and randomized in the study. Subject will be randomized to the following treatment groups: 
 
• 300 Subjects to IDP-120 Gel, once-daily application
 
• 300 Subjects to IDP-120 Vehicle Gel, once-daily application
 

**Inclusion criteria:**

1. Male or female at least 9 years of age and older;
2. Written and verbal informed consent must be obtained. Subjects less than age of consent must sign an assent for the study and a parent or a legal guardian must sign the informed consent (if subject reaches age of consent during the study they should be re-consented at the next study visit);
3. Subject must have a score of 3 (moderate) or 4 (severe) on the Evaluator's Global Severity assessment at the baseline visit;
4. Subjects with facial acne inflammatory lesion (papules, pustules, and nodules) count no less than 20 but no more than 50;
5. Subjects with facial acne non-inflammatory lesion (open and closed comedones) count no less than 25 but no more than 100;
6. Subjects with two or fewer facial nodules;
7. Females of childbearing potential and females who are pre-menses must be willing to practice effective contraception for the duration of the study. (Effective contraception is defined as stabilized on oral contraceptive for at least 3 months, IUD, condom with spermicidal, diaphragm with spermicidal, implant, Nuvaring, injection, transdermal patch, abstinence or sterile partner.) Females on hormonal contraceptive must have taken the same type for at least three months prior to entering the study and must not change type during the study. Those who have used any hormonal contraception in the past must have discontinued usage at least three months prior to the start of the study. Women who use birth control for acne control only should be excluded.
8. Pre-menses females and females of childbearing potential must have a negative urine pregnancy test at the screening and baseline visits;
9. Subjects must be willing to comply with study instructions and return to the clinic for required visits. Subjects under the age of consent must be accompanied by the parent or legal guardian at the time of assent/consent signing;
10. If a cleanser, moisturizer or sunscreen is needed during the study, subjects must be willing to use only allowed cleansers, moisturizers, sunscreens, or moisturizer/sunscreen combination products (see Appendix 17.2). The subject must agree to use non-comedogenic products (including makeup and shaving products).

**Exclusion Criteria:**

1. Use of an investigational drug or device within 30 days of enrollment or participation in a research study concurrent with this study;
2. Any dermatological conditions on the face that could interfere with clinical evaluations such as acne conglobata, acne fulminans, secondary acne, perioral dermatitis, clinically significant rosacea, gram-negative folliculitis, dermatitis, eczema;
3. Any underlying disease(s) or some other dermatological condition of the face that requires the use of interfering topical or systemic therapy or makes evaluations and lesion count inconclusive;
4. Subjects with a facial beard or mustache that could interfere with the study assessments;
5. Subjects with more than two (2) facial nodules;
6. Evidence or history of cosmetic-related acne;
7. Subject has a history of experiencing significant burning or stinging when applying any facial treatment (eg, make-up, soap, masks, washes, sunscreens, etc) to their face;
8. Female subjects who are pregnant, nursing mothers, planning a pregnancy during the course of the trial, or become pregnant during the study;
9. Use of hormones (eg, Depogen, Depo-Testadiol, Gynogen, Valergen, etc) for less than 12 weeks immediately preceding study entry; Subjects treated with hormones 12 or more consecutive weeks immediately prior to study entry need not be excluded unless the subject expects to change dose, drug or discontinue hormone use during the study;
10. If female, subject has a history of hirsutism, polycystic ovarian disease or clinically significant menstrual irregularities;


11. Treatment of any type of cancer within the last 6 months, with the exception of complete surgical excision of skin cancer outside the treatment area;
 
12. Subject uses medications and/or vitamins during the study which are reported to exacerbate acne (azathioprine, haloperidol, Vitamin D, Vitamin B12, halogens such as iodides or bromides, lithium, systemic or mid-to super-high potency corticosteroids, phenytoin and phenobarbital); Multivitamins, including Vitamin A at recommended daily doses and Vitamin D at stable doses, are acceptable;
 
13. History of hypersensitivity or allergic reactions to any of the study preparations as described in the Investigator's Brochure, including known sensitivities to any dosage form of tretinoin and benzoyl peroxide;
 
14. Concomitant use of potentially irritating over-the-counter products that contain ingredients such as benzoyl peroxide, alpha-hydroxy acid, salicylic acid, retinol or glycolic acids;
 
15. Subjects who have not undergone the specified washout period(s) for the following topical preparations or physical treatments used on the face or subjects who require the concurrent use of any of the following in the treatment area:
 
 
 - Topical astringents and abrasives (including comedone removal strips) on the face	1 week	
 
 - Non-allowed moisturizers or sunscreens on the face	1 week	
 
 - Antibiotics on the face	2 weeks	
 
 - Other topical anti-acne drugs on the face (e.g., BPO, salicylic acid)	2 weeks	
 
 - Soaps containing antimicrobials on the face	2 weeks	
 
 - Anti-inflammatory agents and corticosteroids on the face	4 weeks	
 
 - Retinoids, including retinol on the face	4 weeks	
 
 - Facial procedures, including chemical peel, microdermabrasion, light (PDT, LED) and laser therapy, and acne surgery	4 weeks	
 
 
If the subject requires topical treatment for acne on areas other than the face (e.g., chest and/or back), the investigator may prescribe a product that does not contain tretinoin or BPO, and must be noted in source documents and eCRF;
 
16. Subjects who have not undergone the specified washout period(s) for the following systemic medications or subjects who require the concurrent use of any of the following systemic medications:
 
 
 - Corticosteroids (including intramuscular injections) (inhaled corticosteroids allowed)	4 weeks	
 
 - Antibiotics	4 weeks	
 
 - Other systemic acne treatments	4 weeks	
 
 - Systemic retinoids	6 months	
 
 
17. Subject intends to use a tanning booth or sunbathe during the study;
 
18. Subjects who are unable to communicate or cooperate with the Investigator due to language problems, poor mental development, or impaired cerebral function;
 
19. Subjects with any underlying disease that the Investigator deems uncontrolled, and poses a concern for the subjects safety while participating in the study.
	- Topical astringents and abrasives (including comedone removal strips) on the face	1 week	- Non-allowed moisturizers or sunscreens on the face	1 week	- Antibiotics on the face	2 weeks	- Other topical anti-acne drugs on the face (e.g., BPO, salicylic acid)	2 weeks	- Soaps containing antimicrobials on the face	2 weeks	- Anti-inflammatory agents and corticosteroids on the face	4 weeks	- Retinoids, including retinol on the face	4 weeks	- Facial procedures, including chemical peel, microdermabrasion, light (PDT, LED) and laser therapy, and acne surgery	4 weeks	- Corticosteroids (including intramuscular injections) (inhaled corticosteroids allowed)	4 weeks	- Antibiotics	4 weeks	- Other systemic acne treatments	4 weeks	- Systemic retinoids	6 months
- Topical astringents and abrasives (including comedone removal strips) on the face	1 week																							
- Non-allowed moisturizers or sunscreens on the face	1 week																							
- Antibiotics on the face	2 weeks																							
- Other topical anti-acne drugs on the face (e.g., BPO, salicylic acid)	2 weeks																							
- Soaps containing antimicrobials on the face	2 weeks																							
- Anti-inflammatory agents and corticosteroids on the face	4 weeks																							
- Retinoids, including retinol on the face	4 weeks																							
- Facial procedures, including chemical peel, microdermabrasion, light (PDT, LED) and laser therapy, and acne surgery	4 weeks																							
- Corticosteroids (including intramuscular injections) (inhaled corticosteroids allowed)	4 weeks																							
- Antibiotics	4 weeks																							
- Other systemic acne treatments	4 weeks																							
- Systemic retinoids	6 months																							

Investigational product, dosage and mode of administration:
 
Investigational Product: IDP-120 (tretinoin and benzoyl peroxide [BPO], 0.05%/2.5%) Gel, applied topically to the face, once daily for 12 weeks.
																								

Comparator Product: IDP-120 Vehicle Gel, applied topically to the face, once daily for 12 weeks.
																								

Duration of treatment:
 
12 weeks for all subjects.
																								

Reference therapy, dosage and mode of administration:
 
See comparator product above.
																								

**Criteria for evaluation:****Co-Primary efficacy:**

IDP-120 Gel will be compared to IDP-120 Vehicle Gel.

Co-primary endpoints are:

- (1) Superiority in absolute change from Baseline to Week 12 in mean inflammatory lesion counts
- (2) Superiority in absolute change from Baseline to Week 12 in mean non-inflammatory lesion counts, and,
- (3) Percentage of subjects who achieve at least a two-grade reduction from baseline and are Clear or Almost Clear at Week 12 in the Evaluator's Global Severity Score.

**Secondary efficacy:**

- Percent change in non-inflammatory lesion count from Baseline to Week 12
- Percent change in inflammatory lesion count from Baseline to Week 12
- Percentage of subjects who have at least a 2 grade reduction at Week 12 from Baseline in the Evaluator's Global Severity Score
- Percent change in non-inflammatory lesion count from Baseline to Week 8
- Percent change in inflammatory lesion count from Baseline to Week 8
- Percent change in non-inflammatory lesion count from Baseline to Week 4
- Percent change in inflammatory lesion count from Baseline to Week 4

**Supportive Efficacy:**

- Percent change in non-inflammatory lesion count from Baseline to Week 2
- Percent change in inflammatory lesion count from Baseline to Week 2
- Percentage of subjects who have at least a 2 grade reduction at Week 8 from Baseline in the Evaluator's Global Severity Score
- Percentage of subjects who have at least a 2 grade reduction at Week 4 from Baseline in the Evaluator's Global Severity Score
- Percentage of subjects who have at least a 2 grade reduction at Week 2 from Baseline in the Evaluator's Global Severity Score

**Efficacy Measurements:***Lesion Counts*

At each visit the Evaluator will count the total number of inflammatory lesions (papules, pustules, and nodules) on the subject's face. Nodules will be counted separately but will be included in the total inflammatory lesion count. At baseline, eligible subjects may have no more than two nodules. Nodules will be included in the statistical analysis of inflammatory lesion counts. All inflammatory lesions will be counted at the same time rather than counting papules and pustules separately. The Evaluator will also count the total number of non-inflammatory lesions (open and closed comedones). The same blinded evaluator should perform the lesion counts and EGSS evaluations at all visits from baseline to week 12 for the same subject.

*Inflammatory lesions* are defined as follows:

Papule: An erythematous, raised, palpable lesion less than 5 mm in diameter

Pustule: An erythematous, raised, likely palpable lesion containing white exudate or pus less than 5 mm in diameter

Nodule: A deep-seated, erythematous, firm lesion greater than 5 mm in diameter

*Non-inflammatory lesions* are defined as follows:

Open comedone (blackhead): A widely dilated sebaceous follicle plugged with darkly pigmented sebum

Closed comedone (whitehead): A small, closed sebaceous follicle distended with sebum, with a white appearance

*Evaluator's Global Severity Score (EGSS)*

At each visit the severity will be determined based on evaluator-blinded evaluations of the signs and symptoms of acne vulgaris. Evaluations will be scored on a scale of 0-4, with 0 being clear and 4 being severe. Please see the table below for complete definitions.

Score	Grade	Description
0	Clear	Normal, clear skin with no evidence of acne vulgaris
1	Almost clear	Rare non-inflammatory lesions present, with rare non-inflamed papules (papules must be resolving and may be hyperpigmented, though not pink-red)
2	Mild	Some non-inflammatory lesions are present, with few inflammatory lesions (papules/pustules only; no nodulo-cystic lesions)
3	Moderate	Non-inflammatory lesions predominate, with multiple inflammatory lesions evident: several to many comedones and papules/pustules, and there may or may not be one nodulo-cystic lesion
4	Severe	Inflammatory lesions are more apparent, many comedones and papules/pustules, there may or may not be up to 2 nodulo-cystic lesions

**Safety Assessments:**

Cutaneous safety and tolerability will be evaluated by tabulations of adverse events and Cutaneous Safety and Tolerability Evaluation scores (scaling, erythema, hypo/hyperpigmentation, itching, burning, and stinging) to be assessed at each study visit. Itching, burning and stinging (Cutaneous tolerability) will be reviewed with the subject at each study visit as an average over the period since the previous visit.

Scaling, erythema and hypo/hyper-pigmentation (Cutaneous Safety) will be assessed by the evaluator at each visit. Cutaneous tolerability signs and symptoms that result in the subject requiring a concomitant therapy, interruption of treatment, or discontinuation from the study will be reported as an AE.

At selected sites, standardized photography of the face will be performed.

**Statistical methods:**

All statistical processing will be performed using SAS® version 9.3 or later unless otherwise stated. Statistical significance will be based on two-tailed tests of the null hypothesis resulting in p-values of 0.05 or less. Tests of lesion count superiority will be based on an ANCOVA with factors of treatment and analysis center and the respective Baseline lesion count as a covariate or on ranked data submitted to an ANCOVA with factors of treatment and analysis center and the respective Baseline lesion count as a covariate. The co-primary analysis of the dichotomized EGSS will be based on logistic regression with factors of treatment group and analysis center. The primary method of handling missing efficacy data will be based on estimation using the method of Markov Chain Monte Carlo (MCMC) imputation.

Additionally, a model-based multiple imputation process will be used as a sensitivity analysis to the MCMC imputation. The absolute change in lesion count will also be analyzed using a repeated measures ANCOVA for lesion count data or repeated measures logistic regression model (generalized estimating equations) for the dichotomized EGSS. Finally, a tipping point analysis will be performed for the primary endpoints.

Inflammatory and non-inflammatory lesion counts will be recorded for each Subject at Baseline and at Weeks 2, 4, 8, and 12. The absolute and percent change from Baseline in inflammatory and non-inflammatory lesions will be derived for each Subject at Weeks 2, 4, 8, and 12.

The EGSS will be recorded for each Subject. The EGSS will be dichotomized into “success” and “failure” with a Subject considered a success if the Evaluator’s Global Severity Score at Week 2, 4, 8, and 12 is at least 2 grades less than baseline and Clear or Almost Clear.

*Populations Analyzed:*

An intent-to-treat (ITT) analysis will be conducted on all study subjects. The ITT population will consist of all randomized subjects who were dispensed study drug.

The safety population will be comprised of all randomized subjects who are confirmed to have used the study drug at least once. A per-protocol (PP) analysis will also be conducted. Subjects will be eligible for the PP analysis if they complete the 12-week evaluation without noteworthy study protocol violations (i.e., any Subject or investigator activity that could have possibly interfered with the therapeutic administration of the treatment or the precise evaluation of treatment efficacy). The PP population will include subjects in the safety population who do not meet any of the following criteria:

- Failed any of the inclusion/exclusion criteria;
- Have taken any interfering concomitant medications;
- Did not attend the Week 12 visit;
- Missed more than 1 post baseline study visit prior to Week 12;
- Have not been compliant with the dosing regimen (i.e. Subjects may not miss more than five consecutive days of dosing and must take 80-120% of expected doses. The number of expected doses will be determined for each subjects based on the length of their participation in the study);
- Out of visit window at the 12-week visit.

Subjects who discontinue from the study due to an adverse event related to study treatment or documented lack of treatment effect (and/or worsening of condition) will be included in the PP population. Prior to breaking the blind, other additional criteria may be added to the list to accommodate for unforeseen events that occurred during the conduct of the trial that result in noteworthy study protocol violations.

Approximately 600 subjects with moderate or severe acne will be enrolled and randomized to the following treatment groups:

- 300 subjects to receive IDP-120 Gel, once-daily application
- 300 subjects to receive IDP-120 Vehicle Gel, once-daily application

Subject demographic and baseline characteristics will be summarized by treatment group using descriptive statistics for the ITT, PP, and safety analysis sets.

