## 12 Statistics

All statistical processing will be performed using SAS® version 9.3 or later unless otherwise stated. Statistical significance will be based on two-tailed tests of the null hypothesis resulting in p-values of 0.05 or less.

The primary method of handling missing efficacy data will be based on estimation using the method of Markov Chain Monte Carlo (MCMC) imputation. This method provides robust estimation when the pattern of missingness is arbitrary. Additionally, the estimation will be done

for each treatment group separately so that the pattern of missingness for one group does not influence the estimation of missing data for another group. Groups of complete datasets following the estimation will be concatenated to form analysis datasets for the comparative analyses and subsequent imputation result inference with SAS PROC MIANALYZE. Descriptive statistics will also be derived from the multiply imputed datasets.

Additionally, a model-based multiple imputation process will be used as a sensitivity analysis to the MCMC imputation. The absolute change in lesion count will also be analyzed using a repeated measures ANCOVA for lesion count data or a repeated measures logistic regression model (generalized estimating equations) for the dichotomized EGSS. Finally, a tipping point analysis will be performed for the primary endpoints.

A statistical analysis plan (SAP), describing all statistical analyses will be provided as a separate document. The SAP will be finalized prior to unblinding of the study treatments.

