**EGSS Missing Data Imputation**

A similar procedure will be used for the analyses based on percentage of EGSS successes wherein the ANCOVA analysis is replaced with a logistic regression analysis. Specifically, missing 12 week EGSS values from which the dichotomized EGSS is derived will be estimated by MCMC which does not rely on the assumption of data missing at random. Additionally, the pattern of missing observations in each treatment group cannot influence the missing value estimation in the other because the imputation is being conducted independently for each treatment group.

The missing 12-week EGSS values will be derived for the analysis using the method of Markov Chain Monte Carlo (MCMC) multiple imputation. Multiple imputation and subsequent analysis will involve 3 principal tasks:

1. Create a data set, one for each treatment group, of subjects with observed values and those needing estimation by MCMC. The missing EGSS values in each data set will be filled in using the MCMC method 5 times to generate 5 data sets. The resulting data sets for each treatment arm will be combined into one complete data set by imputation.

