**Syntax:**

```
proc mi data=datain out=dataout seed=&seed. nimpute=5 <options>;
  where trtpn=(1, or 2);
```

```

mcmc chain=multiple;
var baseline week2 week4 week8 week12;
run;

```

2. For each complete data set, the dichotomous success rate (clear or almost clear with a 2-point change from baseline) will be computed. The 12-week imputed EGSS values will be rounded to the nearest integer value prior to evaluating the success rate. Each complete data set will be analyzed with a logistic regression with factors of treatment group and analysis center.
4. The results from these analyses will be combined into a single inference using SAS PROC MIANALYZE.

A total of 2 random seeds will be needed to impute EGSS for the two treatment groups. Those 2 random seeds have been pre-specified by using a random number generator:

- EGSS; IDP-120 Gel: Seed= 923694678
- EGSS; IDP-120 Vehicle: Seed= 802843905

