#### Sensitivity analyses for EGSS

The first sensitivity analysis for the dichotomized EGSS success will use a repeated measures logistic regression model (generalized estimating equations), with dichotomized EGSS success as the dependent variable and treatment, analysis center, and visit (ie, Week 4, Week 8) as independent factors. In this analysis, data from all post-baseline visits will be included with no imputation for missing data.

The second sensitivity analysis will use the model based multiple imputation method to impute missing data for the dichotomized EGSS data. Although the full details will be presented in the SAP, the multiple imputation will involve 3 principal tasks:

1. Missing values will be filled in 5 times to generate 5 data sets. The imputation model used logistic regression with factors of treatment group and analysis center (ie, the imputation model will be the same as the analysis model).
2. Each complete data set will be analyzed with a logistic regression a factors of treatment group and analysis center.
3. Results from these analyses will be combined into a single inference using SAS PROC MIANALYZE.

A total of 1 random seed will be needed. The random seed has been pre-specified by using a random number generator:

- EGSS: Seed= 461039866

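### The first EGSS sensitivity analysis, a GEE on observed visits with no stated weights, needs a stronger missing-data assumption than the primary imputation it is meant to check

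*Combined protocol and SAP*

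**What the plan says.** Section 12.1.10, on EGSS, sets out the analysis: "The first sensitivity analysis for the dichotomized EGSS success will use a repeated measures logistic regression model (generalized estimating equations", with treatment, analysis center and visit as factors. On missing data it adds that "data from all post-baseline visits will be included with no imputation for missing data". The Synopsis (Statistical methods) summarises the same model as a "repeated measures logistic regression model (generalized estimating equations) for the dichotomized EGSS", and the opening of Section 12 does likewise. None of the three places mentions observation weights or a working correlation.

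The primary approach differs. Section 12 states: "The primary method of handling missing efficacy data will be based on estimation using the method of Markov Chain Monte Carlo (MCMC) imputation". For EGSS, the syntax in Section 12.1.9 runs the imputation within each arm on "var baseline week2 week4 week8 week12", so a missing Week 12 score is drawn given the subject's baseline and earlier scores. Section 12.1.9 also says that missing Week 12 scores "will be estimated by MCMC which does not rely on the assumption of data missing at random".

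Two further EGSS checks are planned in Section 12.1.10: a model-based multiple imputation using treatment and analysis center only, and a tipping point analysis for each primary endpoint, for which no method or range is given.

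Section 8.3 lists, among reasons for leaving, an acne flare needing disallowed treatment, worsening condition and lack of efficacy.

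**The concern.** A sensitivity analysis for missing data should relax or vary the primary assumption. This one tightens it. A GEE on the available records treats those still attending as representative of their arm at that visit. The primary imputation asks less: representativeness only among subjects with the same earlier scores. The step shown is a normal-model imputation, which in fact assumes missing at random; if the plan's own description is taken at face value, the gap to the GEE is wider still.

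If the two analyses disagree, a reader cannot tell whether the primary is fragile or the GEE is biased by selective dropout. If they agree, little has been learned about outcome-related dropout. All three co-primaries must succeed (Section 12.1.6), and EGSS success has the least planned power (at least 95%, against more than 99% for the lesion counts, Section 12.8.2), so its sensitivity analyses are likely to be read closely. The power figure says nothing about the size of any bias.

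**Working it through.** **The plan's own figure.** Section 12.8.2 assumes success in 26.6% and 14.3%, two-sided 0.05, 95% power, and gives 293 per arm. With d = 0.123 and mean rate 0.2045:

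n = [1.960 × √(2 × 0.2045 × 0.7955) + 1.645 × √(0.266 × 0.734 + 0.143 × 0.857)]² / 0.123² = (1.118 + 0.927)² / 0.01513 = 276.5.

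The continuity correction gives (276.5 / 4) × [1 + √(1 + 4 / (276.5 × 0.123))]² = 292.5, so 293. The figure reproduces. The same rates give a design log odds ratio of ln(0.266/0.734) − ln(0.143/0.857) = 0.776, the target around which the simulations are set.

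**Why the assumption matters.** The GEE solves Σ D′V⁻¹(Y − μ) = 0 over observed records. With independence working correlation and treatment-by-visit terms, the fitted Week 12 rate is the success proportion among those still attending. It equals the arm's true rate only if attendance is unrelated to earlier EGSS, because earlier and Week 12 EGSS are correlated. Dividing each record by its probability of being observed given the subject's history restores the balance.

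**Size.** Dropout rates and mechanisms are assumptions. A treatment-by-visit term was added to isolate Week 12. Simulation of 40,000 per arm, visit correlation 0.5 to 0.7; in the one-arm cases 17% leave that arm depending on non-improvement at the last visit and 10% leave the other at random:

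| Arm with outcome-related dropout | Full-data log OR | GEE, independence | GEE, exchangeable |
|---|---|---|---|
| Vehicle | 0.753 | 0.709 (−5.8%) | 0.726 (−3.6%) |
| Vehicle | 0.761 | 0.666 (−12.5%) | 0.700 (−8.0%) |
| Active | 0.779 | 0.857 (+10.0%) | 0.837 (+7.4%) |
| Active | 0.806 | 0.925 (+14.8%) | 0.892 (+10.7%) |
| Both, same mechanism | 0.807 | 0.812 (+0.6%) | 0.809 (+0.2%) |
| Both, same mechanism | 0.788 | 0.809 (+2.7%) | 0.806 (+2.3%) |

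A run with 200,000 per arm and the same dropout levels gave 0.63–0.67 against 0.78 (−19% to −14%) and 0.87–0.93 against 0.76–0.78 (about +12% to +22%), with almost no bias under a shared mechanism. A further run put the shared-mechanism bias at 3 to 5%, toward the null.

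**Against the primary method.** With ordinal EGSS, 60,000 per arm and 20% dropout, the full-data rates were 26.5% and 14.0%, difference 12.5 points.

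- Dropout unrelated to EGSS: GEE 12.6, imputation 12.5.
- Worse scores leave in both arms: GEE rates 28.8% and 15.5%, both too high, difference 13.3; the log odds ratio barely moves (0.791 against 0.795). Imputation 12.8.
- Opposite mechanisms in the two arms, a stress case: GEE 7.3 or 17.6 under independence, off by about −2.4 or +3.0 under exchangeable correlation. Imputation 12.8 to 12.9.

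**Which weights work.** Simulation of 60,000 per arm, about 17% outcome-related dropout in one arm and 10% random in the other, independence working correlation. Common weights use one previous-EGSS coefficient for both arms; arm-specific weights add treatment-by-previous-EGSS. Baseline EGSS was left out because simulated dropout did not depend on it.

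| Informative arm, visit correlation | Full data | Unweighted | Common weights | Arm-specific weights |
|---|---|---|---|---|
| Vehicle, 0.5 | 0.800 | 0.691 | 0.722 | 0.806 |
| Vehicle, 0.7 | 0.771 | 0.627 | 0.664 | 0.773 |
| Active, 0.5 | 0.796 | 0.917 | 0.893 | 0.789 |
| Active, 0.7 | 0.772 | 0.940 | 0.909 | 0.775 |

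The share of bias removed by common weights is (0.722 − 0.691) / (0.800 − 0.691) = 28% in the first row, then 26%, 20% and 18%. Arm-specific weights come within 1% of the full-data value in every row.

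**The case against.** The strongest reply is that this GEE is one of three EGSS checks and no decision rests on it. That stands. A reader might infer that the plan has no check on informative dropout; the documents do not support this, because a tipping point analysis is planned for each primary endpoint. That its method is not described is a separate matter. The model-based imputation does not fill the gap, since it too ignores interim EGSS.

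A reader might also infer that dropout will depend on response. The documents support only that it can. Section 8.3 gives possible reasons and applies equally to both arms, Section 9.4 says users of interfering treatments should not be withdrawn, and early leavers are asked to complete the Week 12 assessments. That last request is qualified in Section 8.3 by feasibility, and Section 12.8.6 has no rule assigning an early assessment to Week 12, so it reduces the problem without removing it.

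The magnitudes depend on chosen scenarios. If more vehicle subjects leave for lack of effect, the GEE understates the benefit. Overstatement needs outcome-related dropout mainly on active, which nothing in the documents specifically suggests. The figures also come from a model with a treatment-by-visit term that Section 12.1.10 does not list, so they show the missing-data bias in isolation and are not predictions for the model as written.

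Finally, the absence of weights is inferred from silence, and Section 12 defers to a separate SAP that is not in the supplied text. But Section 12.1.10 fixes the model, factors and data handling, and a GEE is unweighted unless stated otherwise.

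**Conclusion.** The point holds. As written, the first EGSS sensitivity analysis requires dropout to be independent of earlier EGSS given treatment, center and visit, whereas the primary imputation does not. Under assumed dropout of 10 to 17%, the effect on the Week 12 log odds ratio is negligible to about 5% with a shared mechanism and roughly 5 to 20%, either way, with mechanisms that differ by arm. Larger errors need the stress assumptions shown above.

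Two stronger readings should be set aside. The primary result is not affected: this analysis does not enter the success rule, the testing order or the sample size. And weighting does not turn the GEE into a test of informative dropout; it only brings it to the missing-at-random assumption that the primary already makes. The weight is minor to moderate, justified because the repair is cheap.

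**What to change.** In Section 12.1.10, with matching wording in the Synopsis and the opening of Section 12:

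- Weight each GEE record by the inverse of its estimated probability of being observed. Fit the dropout model separately by arm on visit, baseline EGSS and previous-visit EGSS, or jointly with treatment-by-previous-EGSS and treatment-by-baseline-EGSS terms. A common model without these terms would leave most of the bias in place where mechanisms differ by arm.
- Alternatively, fit a mixed-effects logistic model by maximum likelihood, noting that its odds ratio is subject-specific and so not directly comparable with the primary one.
- State that this analysis assumes missing at random, like the primary, and that the tipping point analysis is the check on informative dropout.

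Cost: revised text, one extra model and slightly wider standard errors. The primary analysis, sample size and decision rule stay as they are.
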